9. STATISTICAL CONSIDERATIONS AND ANALYTICAL PLAN

9.1 ANALYSIS SAMPLES

9.1.1 Analysis Populations

The safety sample is defined as all subjects who receive any amount of the placebo or the brentuximab vedotin study drug. They will be summarized and compared according to the treatment actually received. Because participants receive their assigned medication on the day of randomization, this is conceptually equivalent to the standard intention to treat analysis population.

Supplementary per protocol (PP) analysis samples are defined as follows:

- PP12: Treated participants who receive at least 4 of the 5 infusions over the first 12 weeks, and who have no major protocol deviations that would affect the safety outcomes through the first 12 weeks.
- PP24: Treated participants who receive at least 7 of the 8 infusions over the first 21 weeks, and who have no major protocol deviations that would affect the safety outcomes through the first 24 weeks.
- PP36: Treated participants who receive at least 7 of the 8 infusions over the first 21 weeks, and who have no major protocol deviations that would affect the safety outcomes through the first 36 weeks.
- PP48: Treated participants who receive at least 7 of the 8 infusions over the first 21 weeks, and who have no major protocol deviations that would affect the safety outcomes through the first 48 weeks.

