3. STUDY DESIGN

3.1 DESCRIPTION

This trial will be conducted as a multicenter prospective double blind placebo-controlled dose escalation safety study with brentuximab vedotin and stable background immunosuppressive therapy in adult individuals with dcSSc. Adult male and female participants with dcSSc will be recruited by a collaborative group of clinical sites in the United States. Participants who meet the eligibility criteria will be enrolled without regard to gender, race, or ethnicity. Eligible participants will be randomly assigned to study treatment, either brentuximab vedotin or placebo equivalent in a 6:2 ratio favoring brentuximab vedotin. Three dose cohorts are planned with 8 participants in each cohort, for a total of 24 participants who receive sufficient doses of the investigational medication to assess safety (Section 4.5).

The doses planned for each ascending dose cohort include 0.6mg/kg, 1.2 mg/kg, and 1.8 mg/kg brentuximab vedotin or placebo equivalent. All cohorts will receive intravenous administration of study medication every 3 weeks for 21 weeks, for a total of eight doses. Following completion of treatment, participants will undergo follow-up visits at weeks 24, 28, 36 and 48.

After completion of the first 12 weeks of treatment for each of the first two cohorts of 8 participants, an interim safety analysis will be conducted and reviewed by an independent Safety Review Committee, as described in Section 8.11.2. Approval by the Safety Review Committee following the 12-week interim safety analysis will be required before proceeding to the next higher dose of brentuximab vedotin.

Interim safety analysis will also be conducted at 24 weeks following completion of study treatment for each of the first two cohorts of 8 participants. Following either the week 12 or the week 24 interim safety reviews, the Safety Review Committee can recommend actions regarding study conduct, as described in Section 8.11.2.

[figure not shown]

Figure 1. Study Schema

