8.11.2 Protocol-Defined Interim Safety Reviews

Interim safety reviews will be undertaken by a Safety Review Committee (SRC) comprised of a subgroup of the DSMB. The study design (section 3.1) specifies interim safety analysis and review by the SRC after each of the first two dosing cohorts have completed 12 weeks of therapy. Approval by the SRC is required following review of the 12-week interim safety data prior to proceeding to the next higher dosing cohort.

Interim safety analysis will also be conducted after each of the first two dosing cohorts have completed 24 weeks of therapy.

Following each protocol-specified interim safety review, the SRC can recommend actions regarding study conduct, including, but not limited to, the following:

- 1. Continue the study as planned.
- 2. Add participants to an existing dosing cohort.
- 3. Reduce the number of weeks of study drug administration for the next higher dosing cohort.
- 4. Stop the study.

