9.2.3 Analysis of Dose-Response Relationship

The 3 dosing cohorts will be merged together to determine if there is a significant dose-response relationship in the endpoints with the amount of brentuximab vedotin received. The 4 dose levels include placebo (0.0 mg/kg), and brentuximab vedotin at low (0.6 mg/kg), medium (1.2 mg/kg), and high dose (1.8 mg/kg). The primary endpoint as well as the proportions of participants with peripheral neuropathy and the different types of adverse events will be analyzed using the exact version of the Cochran-Armitage test for trend. Additionally, these endpoints will be analyzed using a logistic regression model. For FVC and the disease severity scales, the Spearman correlation will be used to determine if there is an association in the change from baseline with the dose level. These analyses will be performed on the safety sample and the PP48 sample.

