9.3 SAMPLE SIZE

No formal power analyses were conducted since all safety and efficacy evaluations are exploratory. The total sample size for this study is 24 participants with 8 participants in each of 3 dosing cohorts including 6 participants receiving brentuximab vedotin and 2 receiving placebo. The ability to detect significant events of certain frequencies was considered. Table 2 illustrates the probability of observing at least 1 significant event in a dosing cohort of 6 participants receiving brentuximab vedotin. A cohort of 3 participants has also been included in case there are partially enrolled cohorts.

Table 2 Probability of Events

	True Probability of Event			
	0.1	0.2	0.3	
Probability of observing at least 1 event in 3 participants	0.27	0.49	0.66	
Probability of observing at least 1 event in 6 participants	0.47	0.74	0.88	

Additionally, Table 3 displays the upper and lower limits of the exact 95% Clopper-Pearson confidence interval for the primary outcome among the 6 participants treated with brentuximab vedotin in any dosing cohort.

Table 3 Confidence Limits

Number with Grade 3+ AE	Proportion with Grade 3+ AE	Lower Limit for Exact 95% CI	Upper Limit for Exact 95% CI
0	0.000	0.000	0.459
1	0.167	0.004	0.641
2	0.333	0.043	0.777
3	0.500	0.118	0.882
4	0.667	0.223	0.957
5	0.833	0.359	0.996
6	1.000	0.541	1.000

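### If a cohort's course is shortened by two or more infusions, the fixed 7-of-8 rule leaves PP24, PP36 and PP48 empty for that cohort

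*Protocol*

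**What the plan says.** Protocol section 3.1 gives every cohort the same course: "every 3 weeks for 21 weeks, for a total of eight doses". Sections 3.2 and 5.1.3.1 repeat it.

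Section 8.11.2 lists what the SRC may recommend after an interim safety review of either of the first two cohorts. One listed action is: "Reduce the number of weeks of study drug administration for the next higher dosing cohort". The size of the reduction is not limited.

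Section 9.1.1 defines the safety sample as everyone who received any study drug or placebo, and adds supplementary per-protocol samples. The exposure part of PP24, PP36 and PP48 is the same in all cohorts: "Treated participants who receive at least 7 of the 8 infusions over the first 21 weeks". PP12 has its own count: "Treated participants who receive at least 4 of the 5 infusions over the first 12 weeks". None of these definitions refers to the number of infusions planned for a cohort.

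Three sections use the samples:
- Section 9.2.1 analyses the primary endpoint, within each cohort, on the safety sample and PP48.
- Section 9.2.2 analyses the secondary and exploratory endpoints on the safety sample and on the per-protocol sample matching each week.
- Section 9.2.3 merges the cohorts into four dose levels (0.0, 0.6, 1.2 and 1.8 mg/kg) and says: "These analyses will be performed on the safety sample and the PP48 sample".

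**The concern.** The protocol foresees a change in course length but fixes its per-protocol populations so that they cannot follow it. A per-protocol sample should hold the participants who took the regimen they were meant to take. Under the present wording, a cohort given a sufficiently shortened course is excluded as a whole because its planned regimen falls below the threshold, whatever its participants did.

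The supplementary analysis of the primary endpoint would be lost for that cohort. The supplementary dose-response analysis would lose one of its dose levels. A shorter course would plausibly be recommended because lower-dose data raised a concern, which is when a per-protocol reading of the next cohort would be wanted.

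**Working it through.** **Inputs**
- Dosing every 3 weeks from week 0 to week 21 (section 3.1).
- Threshold for PP24, PP36 and PP48: 7 infusions, the same in every cohort (section 9.1.1).
- Threshold for PP12: 4 infusions by week 12 (section 9.1.1).
- Planned size, section 9.3: "8 participants in each of 3 dosing cohorts including 6 participants receiving brentuximab vedotin and 2 receiving placebo".
- Length of a shortened course: not given, so every case from 8 down to 4 infusions is shown. This does not suggest any course length.

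**Step 1: reproduce the plan's own count.** Weeks 0, 3, 6, 9, 12, 15, 18, 21 give 21/3 + 1 = 8 infusions, of which 12/3 + 1 = 5 fall by week 12. Both agree with the protocol.

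**Step 2: can the threshold be reached?** With k infusions planned, a participant receives at most k, so the threshold can be met only if k ≥ 7. The number that may be missed is k − 7.

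| Planned infusions k | Last infusion (week) | PP24/36/48 reachable? | Doses that may be missed | PP12 reachable? |
|---|---|---|---|---|
| 8 | 21 | yes | 1 | yes |
| 7 | 18 | yes | 0 | yes |
| 6 | 15 | no | – | yes |
| 5 | 12 | no | – | yes |
| 4 | 9 | no | – | yes |

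The whole cohort is lost only when two or more infusions (six weeks or more) are removed.

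**Step 3: size of the loss.** Each cohort has 6 active + 2 placebo = 8 participants.
- Primary endpoint on PP48, affected cohort: 0 of 8.
- Dose-response on PP48, Cohort 3 affected: at most 24 − 8 = 16 participants. These are 6 − 2 = 4 placebo, 6 at 0.6 mg/kg and 6 at 1.2 mg/kg, so three levels remain and the range ends at 1.2 mg/kg.
- Dose-response on PP48, only Cohort 2 affected: again at most 16, at 0, 0.6 and 1.8 mg/kg.
- PP24 and PP36 do not enter the dose-response analysis. Their loss affects the week 24 and week 36 endpoints of section 9.2.2.

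**Step 4: one infusion removed.** The cohort stays eligible but loses its one-dose tolerance. As an illustration, assume each planned infusion is given independently with probability q. The chance of meeting the threshold is q^8 + 8·q^7·(1 − q) with 8 planned and q^7 with 7 planned. Multiplying by 6 gives the expected number of active participants who qualify on exposure.

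| q (assumed) | 8 planned | 7 planned |
|---|---|---|
| 0.99 | 6 × 0.997 = 5.98 | 6 × 0.932 = 5.59 |
| 0.95 | 6 × 0.943 = 5.66 | 6 × 0.698 = 4.19 |
| 0.90 | 6 × 0.813 = 4.88 | 6 × 0.478 = 2.87 |

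The protocol gives no value for q. Steps 2 and 3 do not depend on it.

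**The case against.** The strongest reply is that the SRC only recommends. Eight doses are fixed for every cohort in sections 3.2 and 5.1.3.1, and section 9.4 requires a protocol or SAP amendment for any change in the principal features of design or analysis. A shorter course would therefore probably come with an amendment, and the per-protocol definitions could be revised in it. This weakens the point without removing it. Section 9.4 opens that route but does not require the per-protocol rule to be revised. A revision made then would redefine an analysis population after interim safety data had been reviewed.

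It is also fair to say that the per-protocol samples are labelled supplementary, that section 9.3 calls all evaluations exploratory, and that the safety sample keeps every treated participant in both the primary and the dose-response analyses. All of this stands and limits the severity.

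A reader might infer more than the documents support:
- **Any shortening removes the cohort.** It does not: a 7-infusion course still qualifies.
- **The trend test suffers a known loss of power.** The protocol gives no event rates. Comparing four levels with three would also assume that the full-course event rate persists after dosing is cut. No power figure is justified.
- **The dose scores would be in the wrong order.** Section 9.2.3 speaks of a "dose-response relationship in the endpoints with the amount of brentuximab vedotin received", and five infusions of 1.8 mg/kg total 9.0 mg/kg, less than eight of 1.2 mg/kg (9.6 mg/kg). But the same section goes on to list its levels in mg/kg per infusion. That is a legitimate score, and the documents do not say whether risk follows dose per infusion or cumulative dose.
- **The replacement rule in section 4.5 conflicts with a shorter course.** That rule concerns participants who discontinue early. Completing a shorter planned course is not discontinuing, so no conflict is shown.

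**Conclusion.** The point holds in a limited form. If the planned course of Cohort 2 or Cohort 3 is cut by two or more infusions and section 9.1.1 stays as written, PP24, PP36 and PP48 contain none of that cohort's participants, however compliant they are. PP12 remains reachable as long as at least four infusions are planned by week 12.

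The conclusion rests on the threshold being read literally as a count of seven. The figure of at most 16 of 24 also assumes the planned cohort sizes, with no replacements or added participants, and that only one cohort is shortened that far. It is an upper bound, because missed doses and major deviations would remove more.

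Severity is minor. The contingency may never arise, and the safety-sample analyses are unaffected. It is still worth correcting, because the protocol itself names the action that makes its rule fail.

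**What to change.** In section 9.1.1, define the exposure part of PP24, PP36 and PP48 relative to the infusions planned for the participant's own cohort, for example no more than one planned infusion missed. State that the planned number is the one in force for the cohort, so that an individual's suspended or omitted doses still count as missed. Make the change before any interim review.

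With 8 infusions planned, missing at most one is the same as receiving at least 7, so the samples do not change if all cohorts keep the full course. The cost is about one sentence in the protocol or SAP. The change takes no position on whether, or by how much, dosing should be shortened.

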5.2.3 Peripheral Neuropathy

Suspend brentuximab vedotin administration if the participant develops a Grade 2 peripheral neuropathy. If the peripheral neuropathy resolves, brentuximab vedotin may be restarted at a lower dose as follows: the affected participant in Cohort 1 will restart brentuximab vedotin at 0.3 mg/kg/dose, in Cohort 2 will restart brentuximab vedotin at 0.6 mg/kg/dose, and in Cohort 3 will restart brentuximab vedotin at 1.2 mg/kg/dose.

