5.2.4 Permanent Discontinuation of Study Medication for Toxicity

Permanently discontinue brentuximab vedotin if any of the following occurs:

- The participant misses > 3 doses of brentuximab vedotin.
- Grade 2 peripheral neuropathy recurs after brentuximab vedotin suspension and dose modification, as described above.
- Grade 3 or greater peripheral neuropathy.
- Grade 3 or greater neutropenia or thrombocytopenia.
- Grade 3 or greater infusion reaction.
- Anaphylaxis, defined as a serious allergic reaction that is rapid in onset and may cause death (see Appendix 2) [79].
- New onset rash consistent with Stevens-Johnson syndrome, toxic epidermal necrolysis, or other drug reaction.
- eGFR $< 30 \text{ ml/min}/1.73 \text{ m}^2$.
- Potential drug-induced liver injury, defined as all three of the following:
 - o ALT or AST elevation > 3 times upper limit of normal (ULN), and
 - Total bilirubin > 2 times ULN, without initial findings of cholestasis (elevated serum alkaline phosphatase), and
 - No other immediately apparent possible causes of ALT or AST elevation and hyperbilirubinemia, including but not limited to viral hepatitis, preexisting chronic or acute liver disease, or the administration of other drugs known to be hepatotoxic.
- Two or more Grade 3 or greater infections, or one Grade 4 infection.

• A suspected case of PML.

A diagnosis of PML should be considered in any participant presenting with new-onset or deteriorating neurological signs and symptoms. The participant should be referred to a neurologist or other appropriate specialist for evaluation. If PML is suspected, this should be immediately reported to the NIAID Medical Monitor. The appropriateness of continuing study medication, while the case is being assessed, should be discussed.

If brentuximab vedotin is discontinued, the procedures in Section 4.3 should be followed.

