9.2 ANALYSIS OF ENDPOINTS

9.2.1 Primary Endpoint

For each dosing cohort, the primary endpoint is the proportion of participants who experienced at least one Grade 3 or higher adverse event at or before week 48. It will be analyzed using the safety sample and the PP48 analysis sample. Proportions will be estimated by treatment group together with their 95% confidence intervals derived using the Clopper-Pearson exact method. Although this study is not powered to detect it, a between-group comparison within each dosing cohort will be performed using Fisher's exact test.

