9.2.2 Secondary and Exploratory Endpoints

Secondary and exploratory endpoints consist of the following:

1. The proportion of participants who experience at least one Grade 3 or higher adverse event at or before weeks 12, 24 and 36.

Protocol ITN075AI: BRAVOS Brentuximab Vedotin for Systemic Sclerosis

- 2. The proportion of participants who experience at least one Grade 2 or higher adverse event at or before weeks 12, 24, 36, and 48.
- 3. The proportion of participants with Grade 2 or higher peripheral neuropathy at or before weeks 12, 24, 36, and 48.
- 4. The proportion of participants with Grade 3 or higher neutropenia at or before weeks 12, 24, 36, and 48.
- 5. The proportion of participants with any of the following Grade 3 or higher adverse events at or before week 48:
 - a. Peripheral neuropathy.
 - b. Neutropenia.
 - c. Infectious adverse events.
 - d. Infusion reactions, including anaphylaxis and new onset rash consistent with Stevens-Johnson syndrome, toxic epidermal necrolysis, or other drug reaction.
 - e. PML.
- 6. Modified Rodnan Skin Score (mRSS) at weeks 12, 24, and 48.
- 7. Provisional American College of Rheumatology Combined Response Index in Systemic Sclerosis (CRISS) at weeks 24 and 48.
- 8. Percent predicted Forced Vital Capacity (FVC) at weeks 24 and 48 weeks.
- 9. Physician's global assessment on a Likert scale at weeks 24 and 48.
- 10. Patient's global assessment on a Likert scale at weeks 24 and 48.
- 11. Health-related quality of life (HRQOL) assessed by PROMIS-29 version 2.0 at weeks 24 and 48.
- 12. Physical function assessed by the Scleroderma Health Assessment Questionnaire-Disability Index (SHAQ-DI) at weeks 24 and 48.

All secondary and exploratory endpoints at all study weeks will be analyzed using the safety sample. Additionally, endpoints at weeks 12, 24, 36 and 48 will be analyzed using the corresponding PP12, PP24, PP36 and PP48 analysis samples.

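### The per-protocol samples are defined by infusions received, with no exception for doses withheld for toxicity, so the per-protocol toxicity analyses are selected on the outcome

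*Protocol*

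**What the plan says.** Section 9.1.1 defines a safety sample of everyone who receives any study treatment, and four supplementary per-protocol samples. The last of these reads "PP48: Treated participants who receive at least 7 of the 8 infusions over the first 21 weeks", with the further condition of no major deviation affecting safety outcomes. PP24 and PP36 use the same 7-of-8 count; PP12 requires 4 of the first 5. The reason for a missed infusion plays no part.

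The toxicity analyses are then run on these samples:

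- Primary endpoint (any Grade 3 or higher adverse event by week 48), Section 9.2.1: "It will be analyzed using the safety sample and the PP48 analysis sample".
- Secondary endpoints, Section 9.2.2: "Additionally, endpoints at weeks 12, 24, 36 and 48 will be analyzed using the corresponding PP12, PP24, PP36 and PP48 analysis samples". One of these is "The proportion of participants with Grade 3 or higher neutropenia at or before weeks 12, 24, 36, and 48".
- Dose-response tests, Section 9.2.3: "These analyses will be performed on the safety sample and the PP48 sample".

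Section 5.2 makes the infusion count depend on toxicity. Among the reasons in 5.2.4 for permanent discontinuation is "Grade 3 or greater neutropenia or thrombocytopenia", along with Grade 3 or higher neuropathy, Grade 3 or higher infusion reaction, and two Grade 3 or higher infections or one Grade 4 infection. Section 5.2.3 says "Suspend brentuximab vedotin administration if the participant develops a Grade 2 peripheral neuropathy", and 5.2.1 and 5.2.2 suspend dosing for SARS-CoV-2 infection and for other significant infections or adverse events. Missed doses alone end treatment only under this condition: "The participant misses > 3 doses of brentuximab vedotin".

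**The concern.** An analysis sample for a safety endpoint should not depend on whether the participant had the safety event. Here it does. The toxicities being counted also stop or suspend dosing, dosing determines the infusion count, and the infusion count determines membership.

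The label is also misleading. Someone who misses two or three infusions exactly as Section 5.2 directs has followed the protocol and may stay on treatment, yet is left out of PP24, PP36 and PP48. Section 4.5 does separate reasons for stopping when it decides who is replaced; Section 9.1.1 does not.

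The primary objective is safety, and the protocol commits to a second primary-endpoint estimate and a second dose-trend test on PP48. A low PP48 rate could be read as confirming tolerability among well-exposed participants when it partly reflects removal of those who did not tolerate the drug. If toxicity rises with dose, losing more cases at the higher doses would also flatten the PP48 trend.

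**Working it through.** **The plan's own figures.** Table 2 follows from 1 − (1 − p)^n: for n = 6 and p = 0.1, 0.2, 0.3 this gives 0.47, 0.74, 0.88, as printed. All seven rows of Table 3 reproduce with Clopper-Pearson limits, including 2/6: 0.043 to 0.777. Both tables assume all six treated participants are counted.

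**When exclusion is forced.** Section 5.1.3.1 and Appendix 1 put infusions at weeks 0, 3, 6, 9, 12, 15, 18 and 21, so the 4th is at week 9 and the 7th at week 18.

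| Permanent stop after infusion | PP12 | PP24, PP36, PP48 |
|---|---|---|
| 1, 2 or 3 | out | out |
| 4, 5 or 6 | in | out |
| 7 or 8 | in | in |

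If 5.2.4 is followed, Grade 3 or higher neutropenia starting before week 9 cannot be counted in PP12, and starting before week 18 cannot be counted in PP24, PP36 or PP48. The share of each window closed is 9/12 = 75% (PP12), 18/24 = 75% (PP24), 18/36 = 50% (PP36) and 18/48 = 37.5% (PP48). The same cut-off applies to Grade 3 or higher neuropathy in PP48.

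**Effect on a proportion.** Let p be the true rate, f the share of cases excluded and g the share of non-cases excluded. The per-protocol estimate tends to

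p(1 − f) / [p(1 − f) + (1 − p)(1 − g)],

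which is below p only if f > g. The protocol gives neither f nor g, so the values below are assumptions.

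*Neutropenia.* p = 0.26 is the lymphoma figure in Section 1.4.1.2, borrowed as an assumption. Taking f as the closed share of the window also assumes uniform onset.

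| f | g = 0 | g = 0.1 | g = 0.2 |
|---|---|---|---|
| 0.75 (PP12, PP24) | 0.081 | 0.089 | 0.099 |
| 0.50 (PP36) | 0.149 | 0.163 | 0.180 |
| 0.375 (PP48) | 0.180 | 0.196 | 0.215 |

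*Composite Grade 3 or higher endpoint*, p = 0.40 assumed.

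| f | g = 0 | g = 0.10 | g = 0.19 | g = 0.25 |
|---|---|---|---|---|
| 0.19 | 0.351 | 0.375 | 0.400 | 0.419 |
| 0.375 | 0.294 | 0.316 | 0.340 | 0.357 |

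In the first row the direction reverses once g exceeds f. That can happen if enough participants without a Grade 3 event are excluded, for example after suspension for Grade 2 neuropathy or SARS-CoV-2 infection.

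**One dose group of six, two cases.**

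| Situation | Result | Exact 95% CI |
|---|---|---|
| Safety sample | 2/6 | 0.043–0.777 |
| PP48, one case stopped early | 1/5 | 0.005–0.716 |
| PP48, both stopped early | 0/4 | 0.000–0.602 |
| PP48, one non-case dropped instead | 2/5 | 0.053–0.853 |

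**Trend test.** Exact conditional Cochran-Armitage test, scores 0 to 3, placebo pooled (6) and six per dose. The illustrative data are 0/6, 0/6, 1/6, 3/6. The first p-value column counts outcomes at least as far from the expected score in either direction; the second doubles the one-sided tail.

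| High-dose group after exclusions | Two-sided p | Doubled tail |
|---|---|---|
| 3/6 (none excluded) | 0.025 | 0.025 |
| 2/5 (one case lost) | 0.051 | 0.079 |
| 1/4 (two cases lost) | 0.195 | 0.260 |
| 2/4 (one case, one non-case lost) | 0.039 | 0.052 |
| 3/5 (one non-case lost) | 0.009 | 0.015 |

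**The case against.** The strongest reply is that the protocol already contains the problem. The per-protocol samples are labelled supplementary, every endpoint is also analysed on the safety sample, Section 9.2.6 assigns the safety analyses to that sample, the stopping guidance is event-based, and Section 9.3 calls all evaluations exploratory. An infusion-count threshold is an ordinary way to describe well-exposed participants, and reporting both samples shows any divergence. This stands as a limit on the harm. It does not make the per-protocol toxicity estimate interpretable.

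Other points stand in part:

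- **Composite endpoint.** Neither size nor sign of the bias is established. A single Grade 3 infection does not by itself require permanent discontinuation, and any event costing only one of the eight infusions stays in PP48.
- **Neuropathy timing.** Section 1.4.1.1 gives median onset of 38.0 weeks (about 34 in the phase III trial) for Grade 3 and 27.3 weeks for Grade 2. Many such cases would fall after week 18 and be kept. Those patients could receive up to 16 doses, however, and Section 1.4.1.1.1 gives Grade 3 medians of 15.4 and 16.6 weeks in an older group.
- **Nominal weeks.** Visits have a ±3-day window and laboratory results may be up to 72 hours old at infusion, so the week 9 and week 18 cut-offs can shift by days.
- **Illustrations.** The 26% comes from lymphoma patients, and uniform onset over 48 weeks has no support when dosing ends at week 21. The trend p-values depend on the two-sided convention.

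None of these removes the dependence of membership on the outcome.

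**Conclusion.** The concern holds and should be fixed. Following the plan exactly, early cases of toxicity that permanently stop drug are removed from the per-protocol samples because of the event being counted. That rests only on the definitions and the infusion schedule. For Grade 3 or higher neutropenia, 75%, 75%, 50% and 37.5% of the PP12, PP24, PP36 and PP48 windows are closed.

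For such toxicities the per-protocol proportion is biased low whenever cases are excluded more often than non-cases, which the stopping rule makes likely. For the composite primary endpoint the bias is probably downward, but its size and sign depend on exclusion shares that the protocol does not give. The rates, cohort example and trend p-values show how much one or two exclusions matter with six per dose; they are not predictions. The damage is confined to supplementary results reported beside sound ones.

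**What to change.** Preferred: in Sections 9.2.1 and 9.2.2 analyse the toxicity endpoints on the safety sample only, do the same for the toxicity trend and logistic analyses in 9.2.3, and keep PP12 to PP48 for the exploratory efficacy endpoints. This agrees with Section 9.2.6 and needs no new data.

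Alternative: state in Section 9.1.1 that infusions withheld or stopped for an adverse event or under Section 5.2 do not disqualify a participant from any per-protocol sample. This needs the reason for each missed infusion on the eCRF. It also brings participants with lower exposure into the sample, so that it loses some of its meaning as a well-exposed group.

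Either way the cost is statistical wording in the protocol and matching text in the SAP. No participants or visits are added, and no dosing or discontinuation rule changes.

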4.3 PREMATURE DISCONTINUATION OF STUDY THERAPY

Study treatment, defined as the dosing and administration of study medication according to study specification, will be discontinued for an individual participant if any of the following occurs:

- A toxicity management discontinuation criterion is met for brentuximab vedotin (Section 5.2).
- The participant's dose of methotrexate, mycophenolate mofetil, azathioprine, or prednisone exceeds the allowed dose (Section 5.3.1.1 and section 5.3.3).
- The investigator or the National Institute of Allergy and Infectious Diseases
 (NIAID) medical monitor determines that it is in the participant's best interest to
 discontinue treatment for any reason, including non-adherence to the protocol.
- The participant requests that treatment be halted.
- The participant becomes pregnant (see section 8.8 Reporting Pregnancy).

Further care will be provided according to the judgment and practice of the principal investigator.

At this time the participant will complete all assessments listed for the discontinuation visit (DSC). The participant will be asked to return for safety follow-up visits at weeks 12, 24, 36, and 48, if these visits have not already occurred.

If study treatment is discontinued, the NIAID Medical Monitor should be notified.

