5.3.4 Prohibited Medications and Vaccines

Participants may not use immunosuppressive or immunomodulatory medications, including biologics, except those specified in the protocol. Increases above the dose at study enrollment are prohibited for the following medications:

- Methotrexate.
- Mycophenolate mofetil.
- Azathioprine.

The use of any investigational drug or investigational treatment other than those specified in the protocol is prohibited during study participation. SARS-CoV-2 vaccines and medications used for prevention and treatment of COVID-19, as authorized by the FDA for emergency use, are not prohibited.

The use of live attenuated vaccines is prohibited during treatment with study medication and for 12 weeks following treatment.

Concomitant administration of brentuximab vedotin and bleomycin is contraindicated due to pulmonary toxicity; therefore, bleomycin administration during the study is prohibited.

5.3.4.1 Special Precautions for Cytochrome P450 3A4 Inhibitors or Inducers, or P-glycoprotein Inhibitors

Concomitant use of strong Cytochrome P450 3A4 (CYP3A4) inhibitors or inducers, or P-glycoprotein (P-gp) inhibitors, has the potential to affect the exposure to MMAE. Participants who are receiving strong CYP3A4 inhibitors or inducers, or P-gp inhibitors, should be closely monitored for adverse reactions [55]. See Appendix 3 for examples [80]. These medications should be avoided, and alternatives used whenever possible.

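### The per-protocol samples screen major deviations for their effect on safety only, but are also used for the exploratory efficacy endpoints

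*Protocol*

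**What the plan says.** Protocol 9.1.1 introduces the PP samples with "Supplementary per protocol (PP) analysis samples are defined as follows". Each has two conditions.

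- **Exposure.** PP24, PP36 and PP48 take "Treated participants who receive at least 7 of the 8 infusions over the first 21 weeks". PP12 asks for 4 of the first 5.
- **Deviations.** PP48 takes those "who have no major protocol deviations that would affect the safety outcomes through the first 48 weeks". PP12, PP24 and PP36 use the same test with their own week.

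Section 9.2.2 lists safety endpoints 1 to 5 and efficacy endpoints 6 to 12 (mRSS, CRISS, FVC, physician and patient global assessments, PROMIS-29, SHAQ-DI). It analyses all of them on the safety sample and adds that "endpoints at weeks 12, 24, 36 and 48 will be analyzed using the corresponding PP12, PP24, PP36 and PP48 analysis samples". Section 9.2.3 sets out the trend and logistic analyses of the adverse event endpoints and the Spearman correlation of dose with change in FVC and the severity scales. It closes with "These analyses will be performed on the safety sample and the PP48 sample". No other PP sample is defined for efficacy.

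**The concern.** A per-protocol sample is meant to show the result in people who were treated and assessed as planned, and what counts as a relevant departure depends on the endpoint. Here the relevance test is fixed to safety for every endpoint. Added background immunosuppression is the clear case: it could plausibly move skin score or lung function in the direction hoped for from the study drug. If it is not also judged to affect a safety outcome, the definition keeps that participant in the PP efficacy set. What is at stake is whether the PP efficacy results can be read as results free of major deviations that matter for efficacy. As written, they cannot.

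**Working it through.** The point rests on wording, not on a stated figure. For the record, the plan's figures for a group of six do reproduce: 1 − (1 − p)^6 gives 0.469, 0.738 and 0.882 for p = 0.1, 0.2 and 0.3, against 0.47, 0.74 and 0.88 in Table 2.

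**Step 1: which PP samples meet an efficacy endpoint.** From the endpoint weeks in 9.2.2:

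| Sample | Deviation test | Efficacy endpoints analysed on it |
|---|---|---|
| PP12 | safety, to week 12 | mRSS |
| PP24 | safety, to week 24 | all of 6 to 12 |
| PP36 | safety, to week 36 | none |
| PP48 | safety, to week 48 | all of 6 to 12, plus the 9.2.3 correlations |

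The mismatch therefore matters for PP12, PP24 and PP48.

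**Step 2: does discontinuation under 4.3 close the gap through the infusion count?** Section 4.3 stops study treatment if "The participant's dose of methotrexate, mycophenolate mofetil, azathioprine, or prednisone exceeds the allowed dose", and refers to 5.3.1.1 and 5.3.3 for what is allowed. Two routes remain open.

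- *Increase under the ceiling.* Section 5.3.1.1 gives absolute ceilings, such as methotrexate 25 mg/week. Section 5.3.4 sets a separate, tighter limit: "Increases above the dose at study enrollment are prohibited for the following medications". A participant enrolled below the ceiling and raised to a dose still within it departs from 5.3.4 but does not clearly trigger 4.3, which does not cite 5.3.4. That participant can receive all 8 infusions.
- *Change after the seventh infusion.* Infusions are scheduled at weeks 0, 3, 6, 9, 12, 15, 18 and 21, so the seventh falls at week 18. If the first seven have been given, a later stop still leaves 7 of 8. The period in which the count cannot act is 48 − 18 = 30 weeks, or 30/48 = 62.5% of participation. It includes the week 24 and week 48 efficacy visits. For PP12 the fourth infusion is at week 9, so a stop after that does not breach 4 of 5.

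In both routes only the safety-worded deviation test can remove the participant.

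**Step 3: weight of one retained participant.** Section 9.3 plans 6 active and 2 placebo participants per cohort, 24 in all.

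- Share of a cohort's active group: 1/6 = 17%.
- Share of a cohort's placebo group: 1/2 = 50%.
- Share of the pooled 9.2.3 analysis: 1/24 = 4%.

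The documents give no figure for how far such a deviation would move an outcome. If the participant's mRSS is distorted by b points, the group mean moves by b/n. Assuming b = 3 to 10 for illustration, the shift is 3/6 = 0.5 to 10/6 = 1.7 points in the active group, and 3/2 = 1.5 to 10/2 = 5.0 points in the placebo group.

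**The case against.** The case for leaving the text alone has real force.

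- **Much of the gap may be covered in practice.** The safety outcomes include any Grade 2 or higher adverse event, neutropenia and infections. Extra corticosteroid or immunosuppressant could readily be judged to affect them, and the participant excluded. An excess dose before the seventh infusion can also breach the infusion count through 4.3. This stands as a limit on how often the problem would arise. It does not remove it, because exclusion would then depend on a judgement about safety when the question is efficacy.
- **Little hangs on the result.** The PP samples are supplementary, 9.3 calls all safety and efficacy evaluations exploratory, and efficacy is also analysed on the safety sample. This stands in full.
- **The SAP may refine the definition.** Listing and classifying major deviations is commonly SAP work and is no gap here. The restriction to safety outcomes, however, is fixed in the protocol, and 9.4 requires an amendment to change principal features of the plan.

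Two stronger readings should be resisted. A reader might infer that agreement between the safety-sample and PP efficacy results would give false reassurance, but the protocol nowhere presents that agreement as confirming efficacy. A reader might also argue that wrongly losing one of six participants puts 0.05 out of reach of the within-group signed-rank test. Any exclusion has that effect, including those the fix would add, and the between-group rank-sum test at 6 versus 2 cannot go below 2/28 = 0.071 with nobody removed.

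**Conclusion.** The concern holds in a limited form. The protocol states a deviation test for safety and applies the resulting samples to efficacy, so a major deviation relevant only to efficacy is kept unless the infusion count removes the participant.

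The conclusion assumes that 4.3 is read as citing only 5.3.1.1 and 5.3.3, and that such a deviation occurs and is judged not to affect safety. It cannot be said in advance that the PP efficacy results will be distorted. Nor are the samples without protection, since the infusion count still selects adequately exposed participants. If a deviation is kept, its weight within a cohort is large because the groups are small, but the analyses concerned are supplementary and exploratory. The primary endpoint and the other adverse event endpoints are unaffected, because the safety wording is right for them. This is a minor defect that is cheap to correct.

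**What to change.** In 9.1.1, keep the present deviation test for the adverse event endpoints. For endpoints 6 to 12 of 9.2.2, and for the FVC and severity-scale analysis in 9.2.3, use the same clause with efficacy outcomes in place of safety outcomes, through the matching week, and classify deviations before unblinding. In practice this adds an efficacy version of PP12 (for mRSS), PP24 and PP48. The alternative is to limit the PP samples to the safety endpoints and analyse efficacy on the safety sample alone.

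The cost is a second PP flag in the deviation review and possibly slightly smaller PP efficacy groups. The change concerns analysis samples only and leaves dosing, permitted medication and discontinuation rules as they are.
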